2.7.8 Assess the change from baseline in serum, salivary and/or hair cortisol levels

The actual and percentage change from baseline to each post-baseline visit for serum cortisol, late night salivary cortisol, morning salivary cortisol and hair cortisol levels will be assessed. Descriptive summaries will be provided for every visit in the Core and Extension phases at which the cortisol markers are collected. Salivary cortisol samples will only be included if they are collected within the correct time window. 95% CIs for the percentage change from baseline will also be provided by treatment arms and for all patients.

2.8 Safety analyses

The assessment of safety will be based mainly on the frequency and severity of AEs and on the number of laboratory values that fall outside of pre-determined ranges. Other safety data (e.g. ECG, vital signs, and special tests) will also be presented. All safety outputs will use the SS, which consists of all patients who received at least one dose of osilodrostat or placebo. Safety data will be presented by two different periods in different treatment groups as described below.

- Placebo-control period: osilodrostat arm, placebo arm

- Overall study period: osilodrostat arm, placebo arm excluding placebo-control period, and overall patients (excluding safety data of placebo arm collected during placebo-control period)
 - * Safety summarized during overall study period focuses on safety of osilodrostat treatment, safety of placebo arm is summarized during placebo-control period.

The overall observation period will be divided into three mutually exclusive segments:

- pre-treatment period: from day of patient's informed consent to the day before first dose of study medication
- on-treatment period: from day of first dose of study medication to 30 days after last dose of study medication
- post-treatment period: starting at 31 days after last dose of study medication.

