2.1.1 General definitions

Study drug

Through out the SAP, investigational drug refers to osilodrostat, and study treatment/ study drug refers to osilodrostat or placebo.

Date of study treatment

The start date of study treatment is defined as the first date when a nonzero dose of study treatment was administered and recorded on DAR eCRF. The date of first administration of study treatment in period 1 will be referred as the start date of study treatment.

The last date of study treatment is defined as the last date when a nonzero dose of study drug was administered and recorded on DAR eCRF.

Study day

Study day is used to represent an evaluation, a measurement or an event (e.g. AE onset, laboratory abnormality occurrence, disease progression, etc). The study day is calculated as

Study day = date of assessment –start date of study treatment + 1 (if date of assessment is after start date of study treatment)

Study day = date of assessment –start date of study treatment (if date of assessment is before start date of study treatment)

For any assessment or events such as baseline characteristics or medical history that is supposed to occur prior to start date of the study treatment, study day will be negative. There is no Day 0 defined.

Study day associated with a UFC assessment

The study day associated with a UFC assessment at any particular visit is defined as the study day of the last UFC sample collection for that visit.

Time unit

A year length is defined as 365.25 days. A month length is 30.4375 days (365.25/12). If duration is reported in months, duration in days will be divided by 30.4375. If duration is reported in years, duration in days will be divided by 365.25.

Baseline

Baseline values for efficacy and safety evaluations are defined as the last assessment available before or on the start date of study treatment. If patients have no assessments as defined above, the baseline result will be missing.

Follow up

Regular safety follow-up is scheduled at 30 days after the last date of study treatment. In addition, for patients who discontinued study treatment during Period 1 (Weeks 1 to 12), reasonable efforts should be made to follow the patients and perform the assessments as indicated in protocol visit evaluation schedule table (protocol Table 7-1a) up to and including Week 12. The data collected during the follow up visits in Period 1 will be used as sensitivity analysis for efficacy, and will be used for safety.

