In the SAP, clarification is made that efficacy will be summarized by randomized treatment arms during the placebo-control period. The same analysis will be performed by randomized treatment arms and for overall patients during the open-label period.

Safety will be summarized by randomized treatment arms during the placebo-control period. For the overall study period, only safety data associated with osilodrostat treatment will be summarized, which means safety data in placebo-arm collected during placebo-control period will be excluded from the analysis.

5 Appendix

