2.8 Safety analyses

The assessment of safety will be based mainly on the frequency and severity of AEs and on the number of laboratory values that fall outside of pre-determined ranges. Other safety data (e.g. ECG, findings from Holter recordings, vital signs, and special tests) will also be presented.

In the Final CSR results for the overall study period will be analyzed using the SS. Safety analyses presented for the placebo-control period in the interim CSR will not be repeated. Safety analyses for overall study period will focus solely on the safety of osilodrostat treatment. The analyses include the osilodrostat arm besides the placebo arm excluding placebo-control period, and overall patients (excluding safety data of placebo arm collected during placebo-control period).

The overall observation period will be divided into three mutually exclusive segments:

- pre-treatment period: from day of patient's informed consent to the day before first dose of study medication
- on-treatment period: from day of first dose of study medication to 30 days after last dose of study medication
- post-treatment period: starting at 31 days after last dose of study medication.

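### Overall-period safety tables are described as osilodrostat safety only, yet placebo-arm changes are measured from a baseline about 12 weeks before the first osilodrostat dose

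*SAP*

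**What the plan says.** Core SAP 2.8 presents safety for two periods. The second is defined as "Overall study period: osilodrostat arm, placebo arm excluding placebo-control period, and overall patients", where the pooled group also omits what the placebo arm contributed during Period 1. The section gives the reason: "Safety summarized during overall study period focuses on safety of osilodrostat treatment". Core SAP section 4 lists this as a change from the protocol, adding that "only safety data associated with osilodrostat treatment will be summarized". The final SAP keeps the grouping, again with the "placebo arm excluding placebo-control period" (2.1.1 and 2.8), and is firmer about the purpose: "Safety analyses for overall study period will focus solely on the safety of osilodrostat treatment".

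Both SAPs have one baseline rule, in 2.1.1: "Baseline values for efficacy and safety evaluations are defined as the last assessment available before or on the start date of study treatment". Two further definitions in the same section fix its meaning. The first is "study treatment/ study drug refers to osilodrostat or placebo". The second is "The date of first administration of study treatment in period 1 will be referred as the start date of study treatment". Neither SAP, nor the protocol, defines a separate baseline before the first osilodrostat dose for patients randomised to placebo. The on-treatment period in 2.8 also begins at the first dose of study medication, which in that arm is placebo.

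**The concern.** The exclusion is intended to make the overall-period tables specific to osilodrostat, but a change from baseline has two ends and only one was moved. A placebo-arm patient's post-Week 12 value is compared with a value from before 12 weeks of placebo. The osilodrostat arm is compared with a value taken immediately before the drug. The pooled column combines the two.

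Change during those 12 weeks is plausible on the protocol's own account. Protocol 2.6 names uncontrolled hypercortisolism on placebo as a study risk, 6.3.4 expects symptoms of high cortisol on placebo, and 6.1.3 provides for starting or intensifying treatment of glucose, blood pressure and potassium during Weeks 1-12. Blood pressure, potassium, weight and QT are also among the osilodrostat risks listed in 2.6, so they are quantities these tables will be used to judge. A deterioration on placebo could be read as an osilodrostat effect. A real change on osilodrostat from a different Week 12 state could be masked.

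**Working it through.** The plan gives no figure on this point to reproduce. The check is a chain of definitions, followed by arithmetic for scale.

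**Definition chain (both SAPs, 2.1.1)**

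1. Study treatment is osilodrostat or placebo.
2. Its start date is the first Period 1 administration, in both arms.
3. Baseline is the last assessment before or on that date, for safety as well as efficacy.
4. Placebo-arm patients move to osilodrostat immediately after the Week 12 visit (core SAP 1.1.3), scheduled for Day 85. The gap is 85 - 1 = 84 days, or 12 weeks.

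**Which outputs depend on baseline**

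| Dependent on the baseline value | Not dependent |
|---|---|
| Laboratory shift tables; laboratory changes (core SAP 2.8.3) | Worst post-baseline CTCAE grade, which disregards baseline (2.8.3) |
| QT/QTcF increases over 30 and 60 ms; new threshold crossings; PR and QRS criteria (2.8.4.1) | Hy's Law counts; grade 3/4 listings (2.8.3) |
| Notable blood pressure, pulse and weight; vital-sign shifts and changes (2.8.4.2) | Deaths (2.8.2) |
| Adverse events ongoing across Week 12 and judged as worsening from baseline (2.8.1) | Adverse events first starting after Week 12 (2.8.1) |

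**Share of the pooled column**

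Inputs: 46 osilodrostat and 23 placebo patients planned (core SAP 1.1); placebo-arm discontinuation before Week 12, q, assumed below 50% (core SAP section 3). Only patients who switch contribute, so the placebo-arm weight is w = 23(1 - q) / [46 + 23(1 - q)].

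- q = 0: 23/69 = 33.3%
- q = 10%: 20.7/66.7 = 31.0%
- q = 25%: 17.25/63.25 = 27.3%
- q = 50%: 11.5/57.5 = 20.0%

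A mean drift d between Day 1 and Week 12 enters the placebo-arm column in full and the pooled mean change as w × d.

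**Illustration only: QTcF rise above 30 ms at one visit, placebo-arm patients**

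The predicted maximum mean effect at 30 mg is 6.3 ms (protocol 1.2.1.2.4). The drift d and the SD s of the change are assumptions that the documents do not supply, and changes are taken as normal. The rate is 1 - Φ[(30 - 6.3 - d)/s].

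| Assumed SD | d = 0 | d = +5 ms | d = -5 ms |
|---|---|---|---|
| 10 ms | 0.9% | 3.1% | 0.2% |
| 15 ms | 5.7% | 10.6% | 2.8% |
| 20 ms | 11.8% | 17.5% | 7.6% |

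A modest assumed drift can move the rate noticeably either way. The table does not estimate what happens in this trial.

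**The case against.** The best defence is that a common post-washout, pre-treatment baseline is a recognised choice and is the protocol's own: section 7.1.1.3 makes Day 1 values the study baseline. Results are shown by arm as well as pooled, change on placebo appears in the Period 1 tables, and the grouping is disclosed. This stands for Period 1 and for efficacy. It is weaker for the overall period. Protocol 10.5.3.1 grouped that period by randomised arm without removing placebo-period data, and a Day 1 baseline suits that layout. The SAPs changed the content and purpose of the summary but not the reference value, and gave no reason for keeping it. They did separate the drugs for exposure: core SAP 2.4.1.1 reports placebo and osilodrostat exposure separately, and final SAP 2.4.1.1 excludes placebo exposure.

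A reader might infer that every overall-period safety table is compromised. The documents do not support that. Safety rests mainly on adverse-event frequency and severity and on out-of-range laboratory counts, and most of those need no baseline value. An event that began on placebo falls in the excluded data, and one that begins after Week 12 is new under either baseline.

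A reader might also infer that Week 12 supplies a complete replacement baseline. It does so only in part:

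- Haematology, chemistry and vital signs are scheduled then (protocol Table 7-1a).
- The Week 12 safety ECG is taken 1.5 hours post-dose with no triplicate required, whereas the Day 1 QTcF baseline is the mean of three pre-dose tracings (protocol Table 7-6 and 7.2.2.6.2).
- The Week 12 Holter starts pre-dose but runs for 24 hours and can extend into osilodrostat treatment.
- No pituitary MRI is scheduled at Week 12.
- Core SAP 2.4.1.1 counts the Week 12 visit date as the first day of Period 2 treatment, so a rule based on date alone cannot separate values before and after the first osilodrostat dose.

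**Conclusion.** The mismatch is real and is present in both SAPs. In overall-period outputs that depend on baseline, placebo-arm results combine about 12 weeks of change on placebo with change on osilodrostat. The effect is complete in the placebo-arm column and carries a weight of about 20% to 33% in the pooled column. The upper figure, 23 of 69, assumes that every placebo patient switches; the lower is the limit of the plan's own discontinuation assumption. Both use planned arm sizes with all 46 osilodrostat patients contributing.

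It would be tempting to conclude that the tables overstate osilodrostat toxicity, or understate it. Neither follows: the documents give no Day 1 to Week 12 drift and no variability of change. The osilodrostat-arm column, the placebo-controlled comparison and efficacy are untouched. This is a low-cost improvement in how the safety results can be read, and it does not undermine the trial's main conclusions.

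**What to change.** In both SAPs, add to 2.1.1 a second baseline for placebo-arm patients, used only in overall-period laboratory, vital-sign (including weight) and ECG outputs: the last assessment before the first osilodrostat dose, confirmed by date and time as taken before that dose. In 2.8, start these patients' overall-period on-treatment window at the same dose. Reading worsening from that point also settles how adverse events ongoing across Week 12 are counted.

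Keep the Day 1 baseline for Period 1 and efficacy, and keep the existing baseline for tumour volume, with a footnote that there is no Week 12 MRI. For QTcF, show placebo-arm and pooled results against both the Day 1 triplicate and the Week 12 value, so that the difference in ECG method is visible.

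The cost is one definition, one extra baseline flag and footnotes; no new data are needed. The drawbacks are that two baselines must be explained in the report, and that the re-baselined ECG reference differs in method between the arms.

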2.8.1 Adverse events (AEs)

Summary tables for adverse events (AEs) have to include only AEs that started or worsened during the on-treatment period, the *treatment-emergent* AEs. However, all safety data (including those from the pre and post-treatment periods) will be listed and those collected during the pre-treatment and post-treatment period are to be flagged.

The incidence of treatment-emergent adverse events (new or worsening from baseline) will be summarized by system organ class and or preferred term, severity (based on CTCAE version 4.03 grades), type of adverse event, relation to study treatment.

Serious adverse events, non-serious adverse events and adverse events of special interest (AESI) during the on-treatment period will be tabulated.

All AEs, deaths and serious adverse events (including those from the pre and post-treatment periods) will be listed and those collected during the pre-treatment and post-treatment period will be flagged.

AEs will be summarized by number and percentage of subjects having at least one AE, having at least one AE in each primary system organ class (SOC) and for each preferred term (PT) using MedDRA coding. A subject with multiple occurrences of an AE will be counted only once in the respective AE category. A subject with multiple CTCAE grades for the same preferred term will be summarized under the maximum CTCAE grade recorded for the event.

In AE summaries the primary system organ class will be presented alphabetically and the preferred terms will be sorted within primary SOC in descending frequency. The sort order for the preferred term will be based on their frequency in the osilodrostat arm.

The following adverse event summaries will be produced by treatment; overview of adverse events and deaths (number and % of subjects who died, with any AE, any SAE, any drug reductions/interruptions), AEs by SOC and PT, summarized by relationship (all AEs and AEs related to study treatment), seriousness (SAEs and non-SAEs), leading to treatment discontinuation, leading to dose interruption/adjustment, requiring additional therapy and leading to fatal outcome. In addition, for the summary of serious and non-serious adverse events the number of occurrences will be produced (an occurrence is defined as >1 day between start and prior end date of record of same preferred term).

2.8.1.1 Adverse events of special interest / grouping of AEs

Groupings of AEs of special interest consist of adverse events for which there is a specific clinical interest in connection with osilodrostat treatment (i.e. where osilodrostat may influence a common mechanism of action responsible for triggering them) or adverse events which are similar in nature (although not identical).

An Excel file with the exact composition of the adverse events groupings is available in the CREDI folder “/CREDI Projects/L/LCI699C/Administrative files/CIS (Clinical Information Sciences)/Biostatistics” which is to be used to map reported adverse events to the adverse events groupings. This file is updated periodically after MedDRA update and/or review of accumulating trial data. Prior to database lock, the file will be copied to proper CREDI study specific folder such as RAP folder.

2.8.2 Deaths

All deaths (on-treatment and post-treatment) will be produced by treatment arm, system organ class and preferred term. Post treatment deaths will be flagged

2.8.3 Laboratory data

Laboratory data summaries will include all assessments available for the lab parameter collected no later than 30 days or safety follow-up whichever is later after the last study treatment administration date using data from all sources. All laboratory assessments will be listed and those collected later than 30 days after the last study treatment date will be flagged in the listings.

Grading of laboratory values will be assigned programmatically as per NCI Common Terminology Criteria for Adverse Events (CTCAE) version 4.03. The calculation of CTCAE grades will be based on the observed laboratory values only, clinical assessments will not be taken into account.

CTCAE Grade 0 will be assigned for all non-missing values not graded as 1 or higher. Grade 5 will not be used. For laboratory tests that are graded for both low and high values, summaries will be done separately and labeled by direction, e.g., sodium will be summarized as hyponatremia and hypernatremia.

For laboratory tests where grades are not defined by CTCAE, results will be categorized as low/normal/high based on laboratory normal ranges.

For laboratory tests where grades are defined by CTCAE

- Summary table for AEs of grades 3 or 4
- Worst post-baseline CTCAE grade (regardless of the baseline status). Each patient will be counted only once for the worst grade observed post-baseline.
- Shift tables using CTCAE grades to compare baseline to the worst on-treatment value

For laboratory tests where grades are not defined by CTCAE ,

- Shift tables using the low/normal/high/ (low and high) classification to compare baseline to the worst on-treatment value

In addition, the following laboratory results will be summarized.

- Selected laboratory data will also be displayed by presenting summary statistics of change from baseline value
- Patients meeting categorical liver function test criteria, including Hy's Law criteria for liver injury (ALT or AST > 3 x ULN and TBIL \geq 2 x ULN and ALP < 2 x ULN), e-dish plot may be provided as well

The following listings will be produced for the laboratory data:

- Listing of all laboratory data with values flagged to show the corresponding CTC grades the classifications relative to the laboratory reference ranges
- Listing of notable laboratory abnormalities (i.e. CTC grade 3 or 4 laboratory toxicities).

2.8.4 Other safety data

2.8.4.1 ECG and cardiac imaging data

ECG data will be summarized with

- shift table baseline to worst on-treatment result for overall assessments
- Number and percentage of patients with clinically notable QT/QTcF interval values will be summarized.
- listing of ECG evaluations for all patients with at least one abnormality.

The notable criteria for PR are

- > 200 ms post-baseline and \leq 200 ms at baseline
- Increase > 25% compared to baseline to a post-baseline value > 200 ms

The notable criteria for QRS are

- > 110 ms post-baseline and \leq 110 ms at baseline
- Increase > 25% compared to baseline to a post-baseline value > 110 ms

The notable criteria for QT and QTcF are

- > 450 ms at any post-baseline and \leq 450 ms at baseline
- > 480 ms at any post-baseline and \leq 480 ms at baseline
- > 500 ms at any post-baseline and \leq 500 ms at baseline
- an increase from baseline > 30 ms at any post-baseline
- an increase from baseline > 60 ms at any post-baseline

2.8.4.2 Vital signs

All vital signs data (height (cm), weight (kg), body temperature ($^{\circ}$ C), supine pulse rate (beats per minute), and supine systolic/diastolic blood pressure (mmHg)) will be listed by patient and visit/time, and abnormalities will be flagged on listing. For blood pressure, two measurements are planned to be taken and the average will be used for analysis purpose. Shift table based on notable value will be provided for vital signs. Change over time from baseline will be summarized.

The criteria for clinically notable abnormalities are defined as follows:

Clinically notable elevated values

- Systolic BP: ≥ 180 mmHg and an increase ≥ 20 mmHg from baseline
- Diastolic BP: ≥ 105 mmHg and an increase ≥ 15 mmHg from baseline.
- Supine pulse: ≥ 120 bpm with increase from baseline ≥ 15 bpm
- Weight: Increase from baseline of $\geq 10\%$

Clinically notable below normal values

- Systolic BP: ≤ 90 mmHg and a decrease ≥ 20 mmHg from baseline
- Diastolic BP: ≤ 50 mmHg and a decrease ≥ 15 mmHg from baseline
- Supine pulse: ≤ 50 bpm with decrease from baseline ≥ 15 bpm
- Weight: Decrease from baseline of $\geq 5\%$

Vital signs (supine BP, HR & temperature) reporting of results will include

- shift table baseline to worst on-treatment result
- table with descriptive statistics at baseline, one or several post-baseline time points and change from baseline to this/these post-baseline time points.

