7.2.2.2 Vital Signs

Vital signs include blood pressure and pulse measurements, and body temperature will be assessed according to [Table 7-1a](#), [Table 7-1b](#) and [Table 7-2](#). Pulse and systolic and diastolic blood pressure will be measured using an automated validated device with an appropriately sized cuff according to the following sequence and times at each visit:

1. Supine: two separate recordings after the patient has been supine for a minimum of five minutes
2. Standing: one recording after the patient has been standing for 1 minute and another recording after the patient has been standing for 3 minutes.

These measurements will be used to assess the presence of orthostatic hypotension.

A drop in systolic blood pressure of ≥ 20 mmHg, or in diastolic blood pressure of ≥ 10 mmHg in the supine vs standing measurements, or presence of lightheadedness or dizziness is considered abnormal and should be recorded on the appropriate form (see section 7.2.2.1.1).

Vital sign assessments at screening may be repeated, if necessary, up to a maximum of 3 times.

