7.2.2.6.2 Electrocardiogram (ECG)

Twelve-lead safety ECGs are collected at the study sites according to [Table 7-1a](#), [Table 7-1b](#), [Table 7-2](#), and [Table 7-6](#). At each visit when a study drug dose is administered, the safety ECG should be collected at 1.5 hours post-dose (approximately at the time of C_{max}).

Twelve-lead safety ECGs are collected at the study site using ECG equipment provided by or validated by vendor. This ECG must be read on site by a qualified physician (e.g., the investigator, or another qualified physician such as a consulting cardiologist) at the time they are collected and documented on the ECG eCRF.

Each 12-lead Safety ECG tracing must be labeled with the:

- study number
- patient initials
- patient number
- date and time

and kept in the source documents at the study site. The clock on the ECG machine must be synchronized with the central clock on a daily basis.

Record the following on the eCRF:

- date and time of ECG
- heart rate
- PR interval
- QT and QTcF interval
- QRS duration

The Fridericia QT formula (QTcF) to correct for variations in heart rate must be used for clinical decisions.

The purpose of the safety ECG is to identify patients with clinically significant ECG abnormalities. On the day of the first study drug administration (Day 1), pre-dose ECGs must be done in triplicate. The mean of the QTcF from these 3 tracings is used as the baseline QTcF to be compared with subsequent ECGs.

ECGs with clinically significant abnormalities must be reported on the ECG eCRF. The overall interpretation will be collected with a Yes/No statement to confirm if any clinically significant abnormalities are present which need to be specified further.

A “notable ECG abnormality” is defined as:

- Day 1 only: an increase in QTcF > 30 msec at 1.5 hours post-dose, compared to the mean pre-dose baseline QTcF from the same day
- QTcF > 480 msec with acute cardiovascular risk, as assessed by a consulting cardiologist
- Any QTcF > 500 msec, confirmed by a consulting cardiologist
- QTcF increase > 60 msec from baseline.

Notable ECG abnormalities must be recorded on the Adverse Events eCRF page. If there is a notable abnormality, then a cardiology consult should be obtained as soon as possible, and the Novartis Medical Monitor for this trial notified of the event.

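### Standing blood pressure is measured at each visit to detect orthostatic hypotension, but the named vital-signs outputs are supine only; a by-arm count on the 20/10 mmHg criterion would be a cheap addition

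*SAP*

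**What the plan says.** **Collection.** Protocol 7.2.2.2 requires two supine recordings at each visit and then: "Standing: one recording after the patient has been standing for 1 minute and another recording after the patient has been standing for 3 minutes". The purpose is explicit: "These measurements will be used to assess the presence of orthostatic hypotension". A supine-to-standing drop of at least 20 mmHg systolic or 10 mmHg diastolic, or lightheadedness or dizziness, "is considered abnormal and should be recorded on the appropriate form".

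**Where an abnormal drop goes.** Protocol 7.2.2.1.1 lists orthostatic hypotension as a sign of adrenal insufficiency. Such signs go on the adrenal-insufficiency eCRF and the AE eCRF in Period 1, and on the AE eCRF alone afterwards. Under protocol 6.2.1 the Independent Endocrinologists who titrate the dose see the adrenal-insufficiency entries and the eCRF vital signs.

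**Planned outputs.** In core SAP 2.8.4.2 the listing covers "supine systolic/diastolic blood pressure (mmHg)) will be listed by patient and visit/time", and the summaries are introduced by "Vital signs (supine BP, HR & temperature) reporting of results will include". Protocol 10.5.3.4 and final SAP 2.8.4.2 use the same supine wording for the summaries. Safety in Period 1 is shown by arm (core SAP 2.8): "Placebo-control period: osilodrostat arm, placebo arm".

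**Comparison with QT.** Protocol 7.2.2.6.2 says: "Notable ECG abnormalities must be recorded on the Adverse Events eCRF page". Core SAP 2.8.4.1 adds a count from the measured values: "Number and percentage of patients with clinically notable QT/QTcF interval values will be summarized".

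**The concern.** Osilodrostat inhibits both cortisol and aldosterone synthesis, and protocol 2.6 names adrenal insufficiency and decreased blood pressure as risks. A postural drop is a measured sign of that risk, with a threshold set by the protocol. Period 1 is the only randomized, blinded comparison, yet no vital-signs output there uses the standing readings.

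The AE tables cover the event only in part. Protocol 8.1.1 asks sites to report a diagnosis in preference to its component signs. It also treats an abnormal test result as an AE only if it is symptomatic, clinically significant, or needs therapy or a change in study medication; a site could read that as excluding an asymptomatic drop. Neither SAP plans an output from the Period 1 adrenal-insufficiency signs eCRF. A count derived from the readings would depend less on how sites judge and code events.

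**Working it through.** The plan states no figure on this point, so there is nothing to reproduce.

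**1. Do any planned numeric criteria compare positions?** From core SAP 2.8.4.1 and 2.8.4.2:
- ECG: PR 2 + QRS 2 + QT/QTcF 5 = 9.
- Vital signs: 4 high + 4 low = 8.
- Total 9 + 8 = 17. Criteria comparing standing with supine pressure: 0.

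**2. Can the supine low-pressure rules stand in?** They require systolic ≤ 90 mmHg with a fall ≥ 20 from baseline, or diastolic ≤ 50 mmHg with a fall ≥ 15 from baseline. Take an illustrative patient with supine 128/80 and standing 104/68:
- Drop: 128 − 104 = 24 (≥ 20) and 80 − 68 = 12 (≥ 10). The protocol's criterion is met.
- Supine 128 > 90 and 80 > 50. Neither low rule is met.

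The drop would be reported only through the site's AE entry, without a mmHg value.

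**3. How much data is there?** Inputs: Period 1 post-baseline visits at Weeks 2, 5, 8 and 12 (protocol Table 7-1a), so 4; planned enrolment 69, split 46 and 23 (core SAP 1.1); two standing readings per visit.
- Patient-visits: 4 × 69 = 276 (4 × 46 = 184 osilodrostat; 4 × 23 = 92 placebo).
- Standing readings: 276 × 2 = 552 (368 and 184).
- Day 1 readings: 69 × 2 = 138.

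These are approximate. Enrolment of 69 is itself approximate, dropout would lower the figures, and unscheduled visits and later periods would add to them.

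**4. Which rule for the drop?** The protocol does not say how two supine and two standing readings are combined, and the choice matters. Suppose there is no true postural change and each diastolic reading has independent normal error with SD *s*. The documents give no such SD, so *s* = 4, 5 and 6 mmHg are assumptions.

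- *Mean supine minus mean standing.* The SD of the difference is s√(1/2 + 1/2) = s. Per visit, p = 1 − Φ(10/s). Over four visits, 1 − (1 − p)⁴.
- *Mean supine minus the lower standing reading.* With M ~ N(0, s²/2), per visit p = E{1 − [1 − Φ((M − 10)/s)]²}, by numerical integration. Over four visits as above.

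| s (mmHg) | Mean rule: p, then any of 4 visits | Lower-reading rule: p, then any of 4 visits |
|---|---|---|
| 4 | 0.0062, 2% | 0.039, 15% |
| 5 | 0.0228, 9% | 0.094, 33% |
| 6 | 0.0478, 18% | 0.155, 49% |

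On the diastolic limb alone, the lower-reading rule would flag far more patients by chance. The same background in both arms would dilute any real difference. Averaging also matches core SAP 2.8.4.2, which averages its paired blood pressure readings.

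**The case against.** The strongest reply is that nothing is broken. Protocol and SAPs agree, and the standing readings already have a use: they feed the adrenal-insufficiency and AE forms, and through them dose titration. AEs are tabulated by arm and preferred term, and separately for those leading to dose interruption or adjustment. Hypocortisolism-related events are a named group of special interest (protocol 8.1.3), so a drop absorbed into adrenal insufficiency should still be counted there, although the exact grouping sits in a file outside these documents. AE entries also carry grade, duration, action taken and outcome. All of this stands, and it keeps the point minor. It does not supply a count based on the measured threshold.

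The QT parallel is imperfect. QTcF has mandatory stopping limits, protocol 10.5.3.4 itself asks for the notable-QTcF count, and some of the AE-recorded ECG abnormalities need a cardiologist's assessment. It shows only that the plan does not regard AE entry as replacing a count of measured values. Laboratory data point the same way: core SAP 2.8.3 grades them from observed values without clinical assessment.

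Two textual cautions also stand. Core SAP 2.8.4.2 opens by referring to all vital signs data before naming supine pressure, so it is not certain that standing values would be left out of the listing. Table 7-1a marks blood pressure for database entry without naming position.

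A reader might infer that the SAP departs from the protocol, or that orthostatic hypotension would go unreported. The documents support neither: the supine wording is the protocol's own, and the AE route exists.

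**Conclusion.** The point holds as a minor improvement to safety reporting. Standing pressure is measured for a stated safety purpose against a stated threshold, and no named vital-signs output or numeric criterion uses it. The existing AE route is indirect and depends on site judgement.

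It would be tempting to read the 276 patient-visits or 552 readings as missed events, or as a ceiling on them. They are neither; they describe roughly what Period 1 would make available. The documents give no rate of postural drop and no share of drops absorbed into a diagnosis, so the number of patients affected cannot be estimated.

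The conclusion assumes that standing values are in the clinical database, which is reasonable but not confirmed. No primary or key secondary conclusion changes.

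**What to change.** In core SAP 2.8.4.2:

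1. Add standing blood pressure at 1 and 3 minutes, and the supine-minus-standing difference, to the vital-signs listing, flagging values that meet the numeric criterion.
2. Add one descriptive table: number and percentage of patients with a drop of at least 20 mmHg systolic or 10 mmHg diastolic at any post-baseline Period 1 visit, by arm and by Day 1 status (drop, no drop, missing).
3. State the rule: mean of the two supine readings minus mean of the two standing readings, separately for systolic and diastolic. Averaging can mask a brief drop at one time point, so the lower-standing-reading version may be shown as a sensitivity display, but no more than that.
4. Use as denominator the patients with at least one post-baseline Period 1 visit at which both positions were recorded.

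Leave the symptom limb (lightheadedness or dizziness) in the AE tables, and say in a footnote that the table covers the numeric limb only. A count for the osilodrostat-treated period is optional and has no concurrent control.

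The cost is SAP wording, an extended listing and one table, with no new data collection if standing values are in the database. The downside is a little programming and partial overlap with the AE tables.
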